Baseline and Follow-up Assessment: After meeting full criteria and consenting to participate in the study participants will be asked to complete 4 psychosocial interviews, T1 (baseline), T2-T4 (follow-ups). The interviews may vary in length and may take up to 2.5 hours to complete, depending on the ability of the participants to answer each question. The following information will be collected:

Primary Outcomes: PC Symptom Burden and HRQoL.

Symptom burden is assessed using the EPIC-Short Form Sexual Summary (EPIC-S) score and the EPIC-Short Form urinary domain score (EPIC-UIN). 168,170,147 HRQoL will be measured with the Functional Assessment of Cancer Therapy-Prostate (FACT-P including 4 domains of the FACT-G)⁴⁰ and PROMIS short forms for pain and fatigue. 148 The FACT-P and PROMIS measures have been used to assess functioning (e.g., nausea, pain, fatigue, life engagement, work and/or daily activities) in cancer survivors and are available in Spanish. 148,149

Possible Moderators of C-CBSM's Effects on our Primary Outcomes.

Socioeconomic Status (SES): We will collect SES by gathering information on household income.

Treatment Type: We will assess treatment type as surgery (e.g., radical retropubic, radical perineal, laparoscopic, robotic assisted), radiation (e.g., external beam radiation therapy; 3- dimensional conformal radiation; intensity modulated; proton beam; brachytherapy), and/ or hormone therapy (e.g., LHRH analogs & antagonists; antiandrogens). We will assess whether SES, and/or type of treatment modify the effects of C-CBSM. We will also explore whether major Hispanic origin categories (e.g., Mexican, Cuban, Puerto Rican, Central & South American) and acculturation moderate the effects of CBSM.

COVID-19 Impact: We will use the COVID-19: Impact of the Pandemic and HRQOL in Cancer Patients and Survivors moderate the effects of the interventions.

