After meeting full criteria and consenting to participate in the study participants will be asked to complete 4 psychosocial interviews. Because the inclusion criteria for this study requires that the participants be Spanish speakers, all participants will be assessed in Spanish by Spanish speaking research staff. Participants complete inperson assessments at baseline (T1) and at approximately (plus or minus 2 months) 3-months (T2), 6- (T3) & 12months (T4) post baseline. The interviews may vary in length and may take up to 2.5 hours to complete, depending on the ability of the participants to answer each question. Participants will have the choice of visiting our study office or conduct the interview at their home or via Zoom or phone if they are not able to meet us in-person. Participants will also be asked at baseline to complete a technology-based questionnaire; this questionnaire will allow research staff to determine the best method to deliver study-related material related to the group sessions. The study-related material will consist of audio files covering relaxation techniques reviewed throughout their 10-week participation. All assessments are completed and scored via RedCap, an online research management tool that enables researchers to create study websites for securely capturing data. RedCap is a web-based system led by the Department of Medical Social Sciences. [name] the PI has extensive experience working with this system. All screening and assessment instruments are guided by our conceptual model for managing PC, have excellent psychometric properties (e.g., Cronbach's $\alpha \ge .70$) and have been translated and validated in Spanish speaking populations.

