To Test Exploratory Hypotheses. Aim 3: For Hypotheses 3, the linear mixed model will include fixed effects for the experimental group (C-CBSM vs. CBSM) and observation time (T1-T4), and random effect for person with a compound symmetry covariance structure for the repeated residuals within person. A group by time interaction and post-hoc tests on this model effect will indicate whether and how the time course of the dependent variable differs between the groups. Hypotheses 1-3 will all be analyzed in a similar manner using the outcome measures described in sections C.6.c (Primary Outcomes), C.6.d (Intervention Targets) and C.6.e (Inflammation) respectively. These measures include markers of symptom burden, systemic inflammation, and cytokine production following cellular activation with TLR ligands. Data from gene expression profiling are analyzed using advanced bioinformatics techniques, and described in C.6.e, and as reported previously by Antoni et al.¹²⁴ As each outcome across the different study hypotheses have been carefully selected to address a priori hypotheses, no adjustment for testing of multiple outcomes will be made. However, within the analysis of a specific outcome, Tukey or Bonferroni adjustment will be made for the multiple tests across different time points. The power calculation below adjusts for this multiplicity. Aims 4a-4c: These hypotheses involve tests of proposed mediators of C-CBSM's effect on our primary outcomes. To test mediation with LGM, individual change trajectory (in each outcome of interest) is characterized by an intercept and a slope factor. The overall pattern of change (e.g., linear, quadratic, etc., as informed by analyses for Aims 1-3) for the whole group can be specified by a particular set of coefficients associated with the slope factor. First, we will specify a growth curve model for all participants with an intercept factor representing our outcome of interest at baseline, and the slope factor reflecting the change trajectory in our outcome measure from T1 to T4. For example, to test that increased stress management skills (e.g., MOCS) in the C-CBSM group accounts for reductions in symptom burden (e.g., EPIC-S), we will first test a LGM model without the stress management skills (the mediator) and then test the model with change in stress management skills from T1 to T4. In the model without the stress management skills, we expect that group assignment is not related to baseline symptom burden, but that group assignment will be related to a greater negative change (reduction) in symptom burden scores. In the next step, we will add stress management skills and expect that after adding this mediator in the model, the path between group assignment and symptom burden slope will become non-significant, while the path between the mediator and symptom burden slope is significant thus suggesting mediation. This approach will be applied to test all mediation models in hypotheses 4a-4c. 191,192 Aim 5a-5b: To evaluate moderators and mechanistic pathways of C-CBSM's effects, we will use LMM and latent variable mediation models. For Hypothesis 5a, we will test moderation by including interaction terms between group assignment (C-CBSM vs. CBSM) and each moderator of interest (e.g., SES, acculturation, Hispanic ancestry, treatment type) within the LMM framework. These models will include fixed effects for group, time (T1-T4), the moderator, and the group × moderator and group × time × moderator interactions. A significant three-way interaction (group × time × moderator) will indicate that change in the outcome (e.g., inflammation, symptom burden, HRQoL) over time differs by both treatment group and the level of the moderator. Post-hoc comparisons will clarify the nature of the moderation effects across timepoints. For Hypothesis 5b, we will test whether improvements in cardiometabolic markers (e.g., lipids, fasting glucose, blood pressure) in the C-CBSM group are mediated by reductions in inflammation using SEM. Parallel process LGMs will estimate trajectories for inflammatory markers and cardiometabolic outcomes across time. The indirect effect from group assignment to cardiometabolic outcome slope via inflammation slope will be tested. This approach allows for simultaneous modeling of changes over time, capturing both within- and between-subject effects. Model fit will be evaluated using standard criteria (CFI > .95, RMSEA ≤ .05, SRMR < .08), and significance of indirect effects will be tested using bias-corrected bootstrapped confidence intervals.

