
Preliminary Analyses and other Statistical Considerations. Descriptive statistics will be computed to ensure values are within expected ranges and to eliminate any errors. We will use PRELIS2^{193,194} to examine multivariate normality. Non-normally distributed variables will be transformed using log transformations. We will compute estimates of internal consistency (Chronbach's α) for all scales and composite scores. If reliability is <.70, we will evaluate the internal consistency of the measure and delete items or subscales as needed.¹⁹⁵

Power Analyses. The primary aim compares pre-post change in symptom burden scores between the randomized arms. A sample of 100 per arm is assumed, although T1-T3 time points will have larger samples. Power is based on the effect size defined as the group difference in the mean change divided by the standard deviation of the change. Power calculations are based on effects of the C-CBSM pilot study. With 100 per arm, there is 80% power to detect an effect size of 0.40 assuming a two-tailed test and a Type I error rate of 5%. Since multiple tests look at change in various post-intervention time points, using a Type I error rate of 1% results in a detectable effect size of 0.49. If effect sizes are calculated from Figure 6 from our preliminary work, then the observed effect sizes as defined above are 0.52 for FACT-G and 0.40 for EPIC-S. Effect sizes for subscales FACT-PWB and FACT-EWB are

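### The low-alpha rule lets items or subscales be dropped from any scale, primary outcomes included, with no algorithm, visit or blinding to arm stated

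*Combined protocol and SAP*

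**What the plan says.** The Preliminary Analyses paragraph of the Data Analysis Plan first sets the scope: "We will compute estimates of internal consistency (Chronbach's α) for all scales and composite scores". It then gives the action: "If reliability is <.70, we will evaluate the internal consistency of the measure and delete items or subscales as needed". Nothing follows on the criterion for choosing an item, the visit at which alpha is judged, whether the same items are kept at all visits, whether the analyst is blind to arm, or whether the published score is still reported.

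The primary outcomes are multi-item instruments. Under Primary Outcomes the protocol lists EPIC-S and EPIC-UIN for symptom burden, and FACT-P (including the four FACT-G domains) with the PROMIS pain and fatigue short forms for HRQoL. The Experimental Design paragraph gives physical, social, emotional and functional domains as examples of primary HRQoL. No section exempts these from the rule.

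Two other statements bear on the point. Under Assessment and Data collection, the instruments are said to have strong psychometric properties, with alpha of at least .70 as the example, and to "have been translated and validated in Spanish speaking populations". Under the exploratory-hypothesis tests, the plan adjusts for multiple time points within an outcome, but "no adjustment for testing of multiple outcomes will be made".

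**The concern.** A primary score should be fixed before the trial data are examined. Here a statistic computed on those data can open the way to a shorter score, and the extent of the shortening is left to judgement. Three things are at stake.

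- **Meaning.** The rule reaches whole subscales. If a FACT-G domain left the total, the primary HRQoL score would no longer cover a domain that the plan names.
- **Validation.** The protocol relies on instruments validated in Spanish speakers. That support belongs to the full instruments, not to versions trimmed on this sample.
- **Discretion.** With no algorithm and no blinding, the text does not rule out a choice made with the group comparison in view. Because there is no adjustment across outcomes, nothing in the plan would absorb the extra error.

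**Working it through.** **1. The plan's own figures.** The power section states 80% power with 100 per arm at a standardised effect of 0.40 (two-sided 5%), and a detectable effect of 0.49 at 1%. Power is approximately Φ(d√(n/2) − z).
- d = 0.40: 0.40 × √50 = 2.828; 2.828 − 1.960 = 0.868; Φ = 0.807.
- d = 0.49: 0.49 × √50 = 3.465; 3.465 − 2.576 = 0.889; Φ = 0.813.

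Both reproduce. The point does not rest on them. They show only that fixing the scoring leaves sample size and power as stated.

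**2. How often would observed alpha fall below .70?** The documents give no true alpha for any scale, so a range is needed. For k parallel normal items and n men, (1 − α)/(1 − α̂) follows an F distribution with n − 1 and (n − 1)(k − 1) degrees of freedom. Hence P(α̂ < .70) = P(F < (1 − α)/.30). The inputs are n = 200 (planned enrolment) and, by assumption, k = 4 or 7.

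| True alpha | (1 − α)/.30 | P(observed alpha < .70), one visit |
|---|---|---|
| .70 | 1.000 | about 51% |
| .72 | 0.933 | 27% to 28% (29% by simulation) |
| .75 | 0.833 | 5% to 6% |
| .78 | 0.733 | 0.3% to 0.5% |
| .80 | 0.667 | 0.02% to 0.04% |

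With the 140 men projected for T4 in the Randomization Protocol, the figure is about 9% to 10% at true alpha .75 and 0.2% to 0.3% at .80.

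**3. What would deletion do to type I error?** This was simulated under no treatment effect: 100 per arm, 4 or 6 equally correlated normal items, a two-sided t-test at 5% on the score at one visit, and 2,500 runs per setting. The Monte Carlo standard error near 5% is √(.05 × .95/2500) = 0.4 percentage points. Item counts and true alphas are assumptions.

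| True alpha | Observed alpha < .70 | Full score | Delete by highest alpha-if-deleted, ignoring arm | Best of full score or any one deletion, chosen on p | Best of full score or up to two deletions, chosen on p |
|---|---|---|---|---|---|
| .60 | over 99% | 5.4% | 4.8% to 5.3% | 10.2% to 10.6% | 16.9% |
| .65 | 92% to 94% | 5.3% to 5.5% | 5.2% | 10.2% to 10.3% | 15.7% to 17.1% |
| .70 | 50% to 52% | 4.5% to 5.4% | 4.8% to 5.2% | 7.4% to 7.6% | 10.4% to 11.1% |
| .80 | none | 4.8% to 5.0% | same | same | same |

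A mechanical deletion that ignores arm leaves the error near 5%. Only a choice made on the treatment comparison raises it. The last two columns are upper bounds on that behaviour: they assume that observed alpha below .70 always opens the choice and that the smallest p-value is always taken.

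**The case against.** The case on the other side has force, and much of it limits the weight of the point.

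- **A low alpha starts an evaluation.** Deletion follows only if the team judges it necessary. This stands: the table in step 2 gives the chance of a review, and the documents support no estimate of the chance of a deletion.
- **The rule sits with preliminary checks.** It appears beside range and normality checks, so the natural reading is that it runs before hypothesis testing. A reader might infer that items would be picked after seeing treatment effects. The text does not say so; it merely fails to prevent it. The same holds for item sets that differ by visit.
- **The instruments are described as reliable.** The .70 is an example and a floor, not a claim that true alphas lie near it. A reader might infer that the rule would fire often, or compound the 5% to 6% over nine scales to reach about 38% to 45%. The documents support neither. At true alpha .80 the same nine-scale sum gives about 0.2% to 0.4%. Independence also fails if the nine are the primary scales, because FACT-P contains the four FACT-G domains.
- **The trigger is internal consistency, not the group difference.** A reader might infer that the rule is biased in itself. Step 3 shows that it is not when arm is ignored.
- **Comparability with the pilot effects.** A reader might infer that deletion would spoil the comparison with the 0.52 and 0.40 behind the power statement. Those effects came from a comparison with a one-day seminar rather than active CBSM, so they were already not a like-for-like benchmark.

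What the objection does not remove is the text itself: all scales are covered, none is exempt, and the choice is unconstrained.

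**Conclusion.** The point holds as a gap in specification that reaches the primary outcomes. The plan permits a change to what a primary score measures on the strength of trial data, and leaves the change to judgement.

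The size depends on reliabilities that the documents do not report. If true alphas are .80 or above, the rule will almost never come into play. If some are near .70, a review is about an even chance at each visit. Inflation of type I error, to about 7% to 11% at true alpha .70 and 10% to 17% at .60 to .65, arises only under the worst-case assumption that deletions are chosen on results. Even a blind deletion would change the content of the score and depart from its validated form.

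The documents do not show that the endpoint is likely to change, that the team intends to choose items on results, or that the rule is biased in itself. The reading of the text is secure; the magnitudes rest on assumed item counts, true alphas and parallel normal items.

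**What to change.** Replace the deletion clause with three statements.

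1. All primary and secondary instruments are scored by their published rules at every visit, whatever the observed alpha.
2. Alpha is reported descriptively for each scale and visit.
3. A reduced-item score may be used only as a labelled sensitivity analysis, with the items chosen on pooled baseline data by someone blind to arm, and the same items then used at every visit and in both arms.

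The cost is SAP wording only. Sample size and power are unchanged. If the instruments are as reliable as the protocol says, nothing is lost by removing the rule; if they are not, the primary scores still mean what the protocol says they mean.

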This project will involve voluntary participation of approximately 200 men treated for a primary diagnosis of localized prostate cancer (PC; Stages1-3, NO, MO) within minimum of 1 month and maximum of -96 months with no evidence of disease recurrence. All participants will be self-identified Hispanics/Latinos (hereafter referred to as Hispanic) of any racial category who speak Spanish or are bilingual but express interest in a Spanish intervention program. We anticipate that about 50% of the population in our target communities is Spanish monolingual or is not proficient in English as these communities have large concentrations of foreign-born Hispanics. Nonetheless, we will also involve participants who are bilingual and agree to participate in a Spanish psychosocial intervention.

Inclusion Criteria:

- ≥ 18 years of age;
- Hispanic/Latino self-identification;

- Study #: 20170656 Effective Date: 8/14/2025
- Spanish speakers (including bilinguals who express interest in a Spanish-based psychosocial intervention);
- Primary diagnosis of localized Prostate Cancer (Stages 1-3, N0, M0);
- Surgical or radiation treatment (e.g., external beam, brachytherapy, proton) within minimum of 1 month and maximum of 96-months;
- Some patients with prior inpatient psychiatric treatment for severe mental illness or overt signs of severe psychopathology (e.g., psychosis) may be enrolled, per P.I. discretion, based on a case-by-case review;
- Willingness to be randomized and followed for approximately 12 months.

Exclusion Criteria:

- History of non-skin cancer within the last 2 years
- Prior inpatient psychiatric treatment for severe mental illness or overt signs of severe psychopathology (e.g., psychosis) within the past six months, as these conditions can interfere with adequate participation in our experimental conditions may be exclusionary, per P.I. discretion, based on a case-by-case review;
- Active alcohol dependence within the past six months may be exclusionary, per P.I. discretion, based on a case-by-case review;
- Active substance dependence within the past six months may be exclusionary, per P.I. discretion, based on a case-by-case review; and
- Acute or chronic immune system medical conditions, medications or conditions that impact immune and endocrine function (e.g., CFS, Lupus, rheumatoid arthritis, Hepatitis C, or immunosuppressive treatment requiring conditions), per P.I discretion, based on a case-by-case review.

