Participants will be randomized by cluster randomization (C-CBSM or CBSM) to balance treatment type across conditions. We project to retain 140 participants at our 12-months post-intervention assessment visit (T4). All participants will be asked to participate in 10-weekly 90-minute in person sessions targeting CBT based skills for managing stress and self-management in one of two experimental conditions—a linguistically translated (Spanish) and culturally adapted cognitive behavioral stress and self-management (CBSM) condition (i.e., C-CBSM) or in a standard version of CBSM that is only linguistically translated (CBSM). Following the baseline visit (T1, pre C-CBSM or CBSM), participants are randomly assigned into one of our experimental or control condition groups.

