Experimental Design. Our primary aim is to examine the effectiveness and incremental efficacy of a 10-week group-based, linguistically and culturally adapted cognitive behavioral stress and self- management intervention (C-CBSM) vs. a linguistically translated standard CBSM (no cultural adaptation) on symptom burden and HRQOL in Hispanic men treated for localized PC. This is randomized control trial (RCT) with a 2x4 design with group assignment (C-CBSM vs. CBSM) as the between-group factor and time (baseline [T1], post-intervention [T2], 6-mos. [T3] & 12-mos [T4]. Post intervention [T4]) as the within-group factor. Primary outcomes are symptom burden (i.e., urinary & sexual function) and HRQoL (e.g., physical, social, emotional & functional). We will make every effort to engage and promote participation in all 10 sessions however we anticipate that some cases will not be able to attend all sessions due to multiple circumstances, such as change in employment or work schedule, health issues, relocation, unforeseen transportation difficulties, family crisis, social/environmental/health crisis (COVID-19), etc. This study uses an intent to treat intervention design model thus participation in all sessions may differ for some individuals. We estimate attrition at ~22% over the study although our prior rate is closer to 10%. Cluster randomization will occur by group type (C-CBSM vs. CBSM).

Experimental Conditions:

CBSM. The standard English language^{59,60} intervention was developed for stress management, risk reduction, health maintenance and self-management by providing relaxation training and CBT-based strategies to improve symptom management, interpersonal adjustment and HRQoL, and reduce arousal and negative mood in men treated for PC. This standard, not culturally-adapted CBSM underwent forward and backward translation by Action Translation Services¹⁷² with internal verification.

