0.81 and 0.42 respectively. With greater effect sizes anticipated in the proposed study, the sample size of at least 100 per arm has sufficient power to detect differences even after adjusting for the analysis of change from baseline to post-intervention time points. Power for C-CBSM's effect on down regulation of inflammatory genes are based on Antoni et al.¹²⁴ study which indicated that the observed effect size was one standard deviation in a sample size of 45 in the experimental condition. Glucocorticoid receptor sensitivity demonstrated similar effects. With a T4 sample size of 100 in the C-CBSM group, effect sizes of 0.48 standard deviations are detectable with 80% power at a 2-tailed Type I error rate of 1%, so that expected effects will be detectable with sufficient power. While pilot data are not available for all outcome measures, the constant in the power calculation regardless of the outcome is the effect size expressed in terms of standard deviations, which is 0.40 or 0.49 depending on whether the Type I error rate is 5% or 1%.

Covariates, Cohort Effects, Intent to Treat & Missing Data. A number of variables (e.g., SES, disease factors) will be considered as possible covariates. These putative confounds will be entered as covariates if correlated with our outcomes (at p<.10). Random assignment should render groups equivalent on covariates and this will be verified post-hoc. We will test differences among cohorts who have completed our conditions by doing an ANOVA within each condition with k levels of cohort. If we find a cohort with differential outcomes (significant Condition x Cohort x Time interaction), we will conduct a Group x Time interaction tested within each cohort, and a Cohort x Time interaction tested within assignment. We have never observed a significant cohort effect in prior CBSM work. We will also use an intent-to-treat approach in that all participants will be retained in the analysis, including those with missing data at time points by using full information maximum likelihood (FIML) estimation. FIML, a recommended state-of-the-art method, 197,198 uses all available data for each participant and provides unbiased estimates of parameters when the data are missing at random.

Cost to the Participants:

There will be no cost to the participants for taking part in this study. All expenses related to the study activities, including laboratory tests done and lab materials.

Risk and Benefits:

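### Power rests on 100 men per arm at 12 months (T4), but the trial enrols about 200 in total and projects 140 retained; at that number, power for the planned effect of 0.40 is about 65%, not 80%

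*Combined protocol and SAP*

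**What the plan says.** The Power Analyses paragraph says: "A sample of 100 per arm is assumed, although T1-T3 time points will have larger samples". It continues: "With 100 per arm, there is 80% power to detect an effect size of 0.40". That figure is for a two-sided comparison at the 5% level. To allow for testing several follow-up visits, it also gives a detectable effect of 0.49 at a 1% error rate. The gene-expression part repeats the sample assumption: "With a T4 sample size of 100 in the C-CBSM group, effect sizes of 0.48 standard deviations are detectable with 80% power". The level there is two-sided 1%. The paragraph calls 0.40 and 0.49 the constants that apply whatever the outcome.

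Three other places give the numbers that bear on this:

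- Participants: "This project will involve voluntary participation of approximately 200 men treated for a primary diagnosis of localized prostate cancer". The opening summary also gives 200.
- Randomization Protocol: "We project to retain 140 participants at our 12-months post-intervention assessment visit (T4").
- Experimental Design: "We estimate attrition at ~22% over the study although our prior rate is closer to 10"%.

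**The concern.** The power paragraph treats 100 per arm as the smallest sample, reached at T4, with more men at T1 to T3. That would need 200 men at T4 and more than 200 at entry. With about 200 enrolled in two balanced arms, 100 per arm is the number at baseline, and any loss takes T4 below it. The paragraph makes no allowance for attrition, although the protocol expects a loss of 22% in one place and, by implication, 30% in another.

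Hypothesis 1 covers change from baseline to each follow-up, including 12 months. The pilot effect for EPIC-S, a primary outcome, is exactly 0.40, so the design has no margin on that outcome. If the T4 number is 70 per arm, the chance of missing an effect of that size at 12 months is about 35% rather than 20%. Because the same two detectable effects are applied to every outcome, the wrong number carries through all of them.

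**Working it through.** **Inputs**

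- Effect size: difference in mean change divided by the SD of change, 0.40 (Power Analyses).
- Two-sided alpha: 5%, and 1% for several visits (Power Analyses).
- Enrolled: about 200, so about 100 per arm (Participants; balanced arms under Randomization Protocol).
- T4 sample: 140 projected (Randomization Protocol), or about 22% loss (Experimental Design).

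**Sample per arm at T4**

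- Projection: 140/200 = 0.70, a 30% loss; 140/2 = 70 per arm.
- Stated attrition: 200 × 0.78 = 156; 156/2 = 78 per arm.
- Prior rate of 10%: 200 × 0.90 = 180; 180/2 = 90 per arm.

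Even the most favourable of these is below 100.

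**Reproducing the plan's figure**

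For a two-sample comparison with n per arm, power ≈ Φ(d√(n/2) − z), where z is 1.96 at 5%. With n = 100 and d = 0.40: 0.40 × √50 = 2.828; 2.828 − 1.960 = 0.868; Φ(0.868) = 80.7%. The exact t-test gives 80.4%. The effects detectable with 80% power by the t-test are 0.398 at 5% and 0.487 at 1%, so the stated 0.40 and 0.49 are reproduced. The 0.48 given for gene expression matches the normal approximation at 1%: (2.576 + 0.842) × √(2/100) = 0.483. The formula is right; it holds only at 100 per arm.

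**Same method at the T4 numbers**

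For n = 70: 0.40 × √35 = 2.366; 2.366 − 1.960 = 0.406; Φ(0.406) = 65.8% (t-test 65.2%). The t-test results are:

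| n per arm | Power for 0.40 at 5% | Power for 0.49 at 1% | Power for 0.40 at 1% | Detectable at 5% | Detectable at 1% |
|---|---|---|---|---|---|
| 100 | 80% | 81% | 59% | 0.40 | 0.49 |
| 90 | 76% | 75% | 53% | 0.42 | 0.51 |
| 78 | 70% | 67% | 46% | 0.45 | 0.55 |
| 70 | 65% | 61% | 41% | 0.48 | 0.58 |

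The plan's 1% claim is for 0.49, so the relevant fall at that level is from 81% to 61% with 70 per arm. Power for 0.40 at 1% was already only 59% at 100 per arm.

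**Enrolment needed for 100 per arm at T4**

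- 22% loss: 200/0.78 = 256.4, so 257 men.
- 30% loss: 200/0.70 = 285.7, so 286 men.

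**The case against.** The strongest reply is that the analysis is not a complete-case t-test. Linear mixed models with full information maximum likelihood keep every randomised man, and earlier visits carry information about a missing T4 value. This has weight. Suppose every man without T4 has an earlier post-baseline value that correlates ρ with the T4 change. The variance of an arm mean, in units of the squared SD, is then about (1 − ρ²)/n + ρ²/100, and its inverse is the effective n. The documents give no ρ, so I assume 0.5 to 0.8.

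- n = 70, ρ = 0.5: 0.75/70 + 0.25/100 = 0.01321, effective n about 76, power about 69%.
- n = 70, ρ = 0.8: 0.36/70 + 0.64/100 = 0.01154, effective n about 87, power about 75%.
- n = 78: effective n about 83 to 91, power about 72% to 76%.

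The shortfall shrinks but remains. These figures are also generous, since some men lost by T4 will have no earlier follow-up.

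Two further replies stand in part. First, the loss is quantified for T4 only. If nearly all 200 men are seen at T2, power for 0.40 at 5% is close to 80% there. The claim of samples above 100 per arm still fails. Second, the consequence differs by outcome. At the pilot FACT-G effect of 0.52, 70 per arm gives 86% power at 5%, though 68% at 1%. For gene expression the plan expects about one SD, and at 1% power exceeds 99% with 70 per arm, so that conclusion survives although its stated sample and detectable effect are wrong. EPIC-S, at 0.40, has no such margin.

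**Conclusion.** The concern holds. The power paragraph uses a T4 sample that the protocol's own enrolment and retention figures rule out, and those retention figures conflict with each other. For an effect of 0.40 at the two-sided 5% level, power at 12 months is 65% on the projected 140 men and 70% at 22% attrition, by the plan's own two-sample method. Allowing for the mixed model under the assumed correlations, it is about 69% to 76%. No reading of the documents reaches 80% at T4.

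The calculations assume equal arms, exactly 200 enrolled and independent observations. Treatment is delivered in groups of 4 to 8; any correlation within groups would lower power further and is a separate matter.

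**What to change.** 1. Choose one retention figure, 140 men or about 22% attrition, and use it in Randomization Protocol, Experimental Design and Power Analyses.
2. Restate power at T4 with that number. By the present method, the effects detectable with 80% power are 0.48 (5%) and 0.58 (1%) with 70 per arm, or 0.45 and 0.55 with 78. If credit is taken for the mixed model, base the calculation on that model and state the assumed correlations and missing-data pattern.
3. Delete the statement that T1 to T3 will have larger samples, and the later reference to at least 100 per arm.
4. Correct the T4 number and the 0.48 in the gene-expression part. The analysed number may be lower still, because blood may be refused or not collected and the monocyte assay needs an in-person draw.
5. Say plainly that at T4 the design does not have 80% power for the pilot EPIC-S effect of 0.40.

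This costs a recalculation and revised wording. The stated power becomes less favourable; enrolment and conduct do not change. Keeping 100 per arm at T4 would instead mean enrolling about 257 to 286 men.
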